9.2 Responsibility for Analyses/In-house Blinding

The statistical analysis of the data obtained from this study will be the responsibility of the Clinical Biostatistics department of the Sponsor.

The Sponsor will generate the randomized allocation schedule for study intervention assignment for this protocol, and the randomization will be implemented in IVRS.

This study will be conducted as a double-blind study under in-house blinding procedures. The official, final database will not be unblinded until medical/scientific review has been performed, protocol deviations have been identified, and data have been declared final and complete.

Blinding procedures related to the planned IA are described in Section 9.7.

PRODUCT: MK-2060

PROTOCOL/AMENDMENT NO.: 007-04

9.3 Hypotheses/Estimation

Objectives and hypotheses are stated in Section 3.

9.4 Analysis Endpoints

9.4.1 Efficacy Endpoints

Primary Efficacy Endpoint

• Time from randomization until the first occurrence of an AVG thrombosis event

Secondary Efficacy Endpoint

• Time to each AVG thrombosis event (first and recurrent) from randomization until the efficacy cutoff date

Efficacy endpoints are further described in Section 4.2.1.1.

9.4.2 Patient-reported Outcome Endpoints

- Mean change from baseline in KDQOL-SF scale scores over time
- Mean change from baseline in EQ-5D scores over time

PRO endpoints are described in Section 4.2.1.2.

9.4.3 Safety Endpoints

• The key safety endpoint is time from randomization until the first ISTH major bleeding event or a clinically relevant non-major bleeding event

Safety and tolerability will also be assessed by clinical review of all relevant parameters including AEs, laboratory safety tests, and vital signs.

Safety parameters are described in Section 4.2.1.3.

9.4.4 Pharmacokinetic Endpoint

The key exploratory PK endpoints for MK-2060 are C_{max} and C_{trough}.

Additional details are in Section 4.2.1.4.

9.4.5 Immunogenicity Endpoints

The exploratory immunogenicity endpoints are the incidence and magnitude (titer) of ADA to MK-2060.

Additional details are in Section 4.2.1.5.

9.4.6 **Pharmacodynamic Endpoints**

aPTT is the key PD endpoint.

PROTOCOL/AMENDMENT NO.: 007-04

Additional details are in Section 4.2.1.6.

9.5 **Analysis Populations**

9.5.1 **Efficacy Analysis Population**

The ITT population will serve as the population for efficacy analyses. All randomized participants will be included in this population. Participants will be included in the treatment group to which they are randomized.

9.5.2 **Patient-reported Outcome Analysis Population**

The PRO population will be the subset of the randomized population based on clinical sites selected for PRO administration. This population consists of all randomized participants at the selected sites who had at least 1 IV administration (including only partial) of study intervention and had completed the baseline and at least 1 post-baseline PRO assessment. The PRO population definition will be applied separately to each questionnaire. Participants will be included in the treatment group to which they are randomized.

9.5.3 **Safety Analysis Population**

Analyses of safety will be performed in the APaT population, consisting of all randomized participants who received at least 1 IV administration (including only partial) of study intervention. Participants will be included in the treatment group corresponding to the study intervention they received for the analysis of safety data. This will be the randomized treatment group for all participants except for those who take incorrect study intervention for the entire treatment period. Such participants will be included in the treatment group corresponding to the study intervention actually received. Any participant who receives both correct and incorrect study intervention will be analyzed according to the randomized treatment group and a narrative will be provided for any events that occur during the IV administration period for which the participant was incorrectly dosed.

At least 1 laboratory or vital sign measurement obtained after at least 1 dose of study intervention is required for inclusion in the analysis of each specific parameter. To assess change from baseline, a baseline measurement is also required.

9.5.4 **Pharmacokinetic Analysis Population**

The population for PK data analysis is defined as all participants with at least 1 measurable PK sample following treatment with MK-2060.

73

9.5.5 Immunogenicity Analysis Population

The population for immunogenicity analysis includes all participants with at least 1 ADA assay result following treatment with MK-2060.

9.5.6 Pharmacodynamic Analysis Population

The primary analysis population for the PD endpoints will be all randomized participants who have at least 1 infusion (including only partial) of study intervention and have at least 1 PD marker assessment. Participants will be included in the treatment group to which they are randomized.

9.6 Statistical Methods

This section describes the statistical methods that address the primary and secondary objectives. Methods related to the exploratory objectives will be described in the sSAP.

P-values for the key secondary efficacy endpoint may be provided as an assessment of strength of evidence without intent to make inferential claims.

For analysis purposes, the baseline assessment is considered the one closest to but before or on the day of randomization (Day 1).

For stratified analyses, the stratification factors used for randomization (Section 6.3.2) will be applied to the analysis. Small strata will be combined in a way specified by a blinded statistician before the analysis, if needed.

Event accrual will be monitored throughout the course of the study. An efficacy cutoff date for the IA or final analysis will be declared when approximately 103 or 171 events, respectively, have accrued for the primary efficacy endpoint. If the study stops at the IA, the Final Efficacy Visits will be scheduled to occur within 14 days of Sponsor's notification to stop the study. If the study continues, the Final Efficacy Visits will be scheduled to occur in the 14 days following the final analysis efficacy cutoff date. All participants still on study treatment at the time of the efficacy cutoff date (Sponsor's notification to stop the study at IA or final analysis) will attend the Final Efficacy Visit with no further administration of study treatment and will have a scheduled Safety Follow-up Visit 90 days after the Final Efficacy Visit. Two database locks will then occur: one using the efficacy cutoff date and another after all safety follow-up data are available. Analyses addressing all efficacy objectives will be performed based on data up to the efficacy cutoff date. Supportive efficacy analyses will be performed including data through the Safety Follow-up Visit. The primary assessment of safety will use all data through the Safety Follow-up Visit. Supportive safety summaries will be provided based on data through the efficacy cutoff date.

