9.6.1.1 Primary Efficacy Endpoint

The nonparametric Kaplan-Meier method will be used to estimate the time from randomization until the first occurrence of an AVG thrombosis event curve in each treatment group. The treatment effect will be assessed by the stratified log-rank test. A stratified Cox proportional hazard model with Efron's method of tie handling will be used to assess the magnitude of the treatment effect (ie, HR) between the treatment arms. The HR and its 95% CI from the stratified Cox model with Efron's method of tie handling and with a single treatment covariate will be reported. *P*-values will be provided to address the primary objective and associated hypothesis (2 pairwise comparisons). Kaplan-Meier figures will also be provided.

Censoring will occur at the last follow-up contact where an AVG thrombosis event could be assessed on or prior to the cutoff date. Any participant who undergoes a kidney transplant during the study will be censored on the date of the kidney transplant.

Efficacy results that will be deemed to be statistically significant after consideration of the Type I error control strategy are described in Section 9.8.

Sensitivity analyses will be described in the sSAP.

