9.7 Interim Analyses

A single IA will be performed to assess efficacy and futility (non-binding). The IA will be conducted by an external unblinded statistician and an external unblinded programmer not otherwise involved in study conduct. Results of the IA will be reviewed by the external DMC, with recommendations provided to an internal executive oversight committee. If the eDMC recommends modifications to the design of the study or discontinuation of the study, the executive committee (and potentially other limited sponsor personnel) may be unblinded to results at the treatment level in order to act on these recommendations. The extent to which individuals are unblinded with respect to results of the IA will be documented by the unblinded statistician. Additional logistical details will be provided in the eDMC Charter.

C Confidential

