10.1.4.1 Executive Oversight Committee

Committees Structure

The EOC is comprised of members of the therapeutic area management. The EOC will receive and decide on any recommendations made by the DMC regarding the study.

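### After a stop at the interim analysis, does Section 9.6 leave open which efficacy cutoff date fixes the reported results?

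*Combined protocol and SAP*

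**What the plan says.** Three sentences in Section 9.6 matter, in this order.

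- The definition: "An efficacy cutoff date for the IA or final analysis will be declared when approximately 103 or 171 events, respectively, have accrued".
- The treatment and visit sentence, which covers everyone still dosed "at the time of the efficacy cutoff date (Sponsor's notification to stop the study at IA or final analysis".
- The sentences on data: "Two database locks will then occur: one using the efficacy cutoff date and another after all safety follow-up data are available", and then "Analyses addressing all efficacy objectives will be performed based on data up to the efficacy cutoff date".

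Between the first two, the section gives separate triggers for the Final Efficacy Visits. After an interim stop they run from the Sponsor's notification. If the study continues they run from the final cutoff.

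Section 9.6.1.1 censors at the last assessable contact up to the cutoff, and Section 9.4.1 ends the recurrent-event window there. P-values "will be provided to address the primary objective and associated hypothesis (2 pairwise comparisons". Section 9.1 attaches one-sided 0.001 to the interim and 0.024 to the final analysis, testing the higher dose first.

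On roles, Section 9.2 says: "The statistical analysis of the data obtained from this study will be the responsibility of the Clinical Biostatistics department of the Sponsor". Section 9.7 says: "The IA will be conducted by an external unblinded statistician and an external unblinded programmer not otherwise involved in study conduct". Section 10.1.4.1 adds: "The EOC will receive and decide on any recommendations made by the DMC regarding the study".

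**The concern.** Read literally, the parenthesis redefines the cutoff as the day the Sponsor tells sites to stop. After an interim stop that day cannot be the day of the 103rd event, because the data monitoring committee must review the results and the executive committee must decide. First events keep accruing in between. The lock and efficacy-analysis sentences follow directly and use the same term.

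The report after a stop could then contain more events than the test that stopped the study. The visible text does not say which threshold would apply to that larger data set. With fixed-order testing, a 20 mg p-value that drifted to 0.001 or above would also end testing of 6 mg. Section 4.2 expects the results to help choose one dose for later studies. A date chosen after the executive committee may have been unblinded would also be open to challenge.

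**Working it through.** **1. The plan's own figures.** Inputs from Section 9.9.1: HR 0.6 for each dose, 103 and 171 first events over three equal groups, one-sided 0.025.

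- Events in one pairwise comparison: 171 × (1 + 0.6)/(1 + 0.6 + 0.6) = 124.4.
- Schoenfeld power: Φ(√124.4 × |ln 0.6|/2 − 1.960) = Φ(2.848 − 1.960) = 81.3%. At 0.024 it is Φ(2.848 − 1.977) = 80.8%, and with both looks 80.9%. The stated 80% is reproduced.
- Interim information: 103/171 = 60.2%, as stated.

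None of these depends on the meaning of the parenthesis.

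**2. The uses of the two dates, side by side.**

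| Place | What fixes the cutoff | Use of the notification |
|---|---|---|
| 9.6, definition | event count | none |
| 9.6, visit scheduling | cutoff date named for the final analysis | visit trigger after an interim stop |
| 1.3, footnote a | event count, with a pointer to 9.7 | visit trigger after an interim stop |
| 8.11.4 | event number reached, cutoff then declared | none |
| 10.8, Table 10, footnote b | event count, with a pointer to 9.7 | visit trigger after an interim stop |
| 9.6, participants still on treatment | the parenthesis | end of dosing and the visit |

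Only the last row equates the two. That sentence concerns dosing and attendance, and nobody can act on an interim stop on the day of the 103rd event because its result is not yet known. The parenthesis merges the two visit triggers given just before it. As a definition of the interim data cut it would be circular, since the notification follows from the interim result.

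**3. How far apart the data sets could be.** The documents give no lag, so 1 to 3 months is assumed. An upper bound on participants still at risk is 489 − 103 = 386. Extra first events = 386 × (1 − exp(−rate × months/12)).

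| Rate per 100 patient-years | 1 month | 2 months | 3 months |
|---|---|---|---|
| 20 (assumed, slow) | 6.4 | 12.7 | 18.8 |
| 50.9 (= 69.4 × 2.2/3, HR 0.6 on both doses) | 16.0 | 31.4 | 46.1 |
| 69.4 (registry rate, Section 4.2) | 21.7 | 42.2 | 61.5 |

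**4. What that does to the results.** Simulated trials had 163 per arm, 13 months' accrual, dropout 0.15 per patient-year, eight strata, HR 1.5 for prior thrombosis, and HR 0.6 for both doses. Accrual, dropout and the prior-thrombosis effect are assumptions. The placebo rate was 0.347 (half the registry rate, since Amendment 04 reports slow accrual) or 0.694 per patient-year. A trial stopped if the 20 mg p-value was below 0.001 at the 103rd event, which happened in about 15–16%.

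- Extra first events at 1/2/3 months: about 6.5/13/19 at half rate and 14/27/40 at the registry rate.
- Mean 20 mg HR at 0/1/2/3 months: 0.409/0.420/0.429/0.436 at half rate and 0.408/0.428/0.446/0.458 at the registry rate.
- SE of log HR: 0.255 to 0.238 at 2 months, half rate.

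**5. Where larger differences come from.** If p<0.001 is applied a second time at the later date, the set of doses below it differs in 17–18%/21–24%/24–27% of stopped trials at half rate and 24%/30%/33% at the registry rate. Over all trials at HR 0.6 that is 0.154 × 0.181 = 2.8% up to 0.160 × 0.333 = 5.3%.

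These shares measure movement around a strict boundary. The 20 mg p-value reaches 0.005 in at most 1.6% of stopped trials at half rate and 2.7% at the registry rate, and 0.024 in at most 0.1%. The second test is also not in the plan: Section 9.1 ties 0.001 to the interim, and Section 9.6 ties the interim to about 103 events.

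**The case for a change.** The best case for acting is that the clash is real, sits in one paragraph, and comes immediately before the lock sentence. The locks follow the Final Efficacy Visits in time, so the first lock is not simply the interim snapshot, and a literal reader could run it to the notification date. Amendment 04 added the efficacy stop, so this branch can occur. A few words written before the interim would remove any suspicion of a date chosen with results in view.

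The wording slip stands. The consequence does not. A lock made later can still use an earlier data cutoff, and the general division of labour in Section 9.2 does not create a fresh significance test for the Sponsor's statisticians. Section 9.6.1.1 sends decisions on significance to Section 9.8. Sections 9.7 and 9.8 are both partly blacked out, so silence in the visible text is not evidence of a gap.

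Section 9.6 also already plans supportive efficacy analyses through the Safety Follow-up Visit, so results with later events will be reported in any case. Section 4.2 makes the results evidence for dose selection without making p<0.001 the selection rule.

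**Conclusion.** No change follows. The parenthesis is a clerical looseness in a sentence about dosing and visits. Every other use of the cutoff points to the event count, and an analyst would cut the efficacy data there. A separate name for the notification date would read better, but that is editorial.

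The interim test at 0.001, overall alpha, power, sample size, visit timing, the primary safety analysis and a study that continues to 171 events are the same under either reading. After an interim stop, using the later date would move the mean 20 mg HR by about 0.01 to 0.05 over assumed lags of 1 to 3 months (0.409 to 0.420 at the least, 0.408 to 0.458 at the most), with a somewhat smaller standard error. Both sets of estimates would be sound. A sentence stating that significance rests on the interim test would repeat what Sections 9.1 and 9.6 already imply.

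The sizes rest on the assumed lag, event rates, dropout, accrual and stratum effect. The conclusion rests on the text and would weaken only if the blacked-out parts of 9.7 or 9.8 prescribed a second formal test after a stop.

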9.6.1 Statistical Methods for Efficacy Analyses

This section describes the statistical methods that address the primary and key secondary objectives related to the efficacy endpoints.

The primary efficacy estimand following the guidance in ICH E9 (R1) [European Medicines Agency 2020] has the following 5 attributes:

- 1. The **treatment** condition of interest and the alternative treatment condition to which comparison will be made: intervention with MK-2060 or placebo.
- 2. The **population** of participants targeted by the clinical question: individuals with ESRD.
- 3. The **variable** (or endpoint) to be obtained for each participant that is required to address the clinical question: first occurrence of an AVG thrombosis event.
- 4. The specification of how to account for **other intercurrent events** to reflect the scientific question of interest: a treatment policy approach will be used for the intercurrent events of discontinuation of study intervention and/or initiation of non-study intervention. No observed data will be excluded from analyses because of these intercurrent events.
- 5. The **population-level summary** for the endpoint which provides the basis for a comparison between treatment conditions: the HR (MK-2060 vs placebo) for the time to first occurrence of an AVG thrombosis event.

9.6.1.1 Primary Efficacy Endpoint

The nonparametric Kaplan-Meier method will be used to estimate the time from randomization until the first occurrence of an AVG thrombosis event curve in each treatment group. The treatment effect will be assessed by the stratified log-rank test. A stratified Cox proportional hazard model with Efron's method of tie handling will be used to assess the magnitude of the treatment effect (ie, HR) between the treatment arms. The HR and its 95% CI from the stratified Cox model with Efron's method of tie handling and with a single treatment covariate will be reported. *P*-values will be provided to address the primary objective and associated hypothesis (2 pairwise comparisons). Kaplan-Meier figures will also be provided.

Censoring will occur at the last follow-up contact where an AVG thrombosis event could be assessed on or prior to the cutoff date. Any participant who undergoes a kidney transplant during the study will be censored on the date of the kidney transplant.

Efficacy results that will be deemed to be statistically significant after consideration of the Type I error control strategy are described in Section 9.8.

Sensitivity analyses will be described in the sSAP.

9.6.1.2 Secondary Efficacy Endpoints

Time to each AVG thrombosis event (first and recurrent)

The primary approach for time to each AVG thrombosis event analysis will be the Andersen-Gill model [Andersen, P. K. 1982] to compare the MK-2060 each dose group to placebo. The Andersen-Gill model is an extension of the Cox proportional hazard model including both first and recurrent events.

For each comparison (MK-2060 vs placebo), treatment group and the stratification factors used for randomization will be included in the model as fixed effects. Robust standard errors will be used to account for correlations of event times within a participant.

Estimates of treatment comparisons and effect size including 95% confidence intervals will be provided based on the fitted model.

The analysis strategy for key efficacy endpoints is outlined in Table 3.

Table 3 Analysis Strategy for Key Efficacy Endpoints

Endpoint	Statistical Method	Analysis Population	Missing Data Approach
Primary Endpoint			
Time from randomization until the first occurrence of an AVG thrombosis event	Test: Stratified log-rank test	ITT	Censor
	Estimation: Stratified Cox model with Efron's tie handling method		
Key Secondary Endpoint			
Time to each AVG thrombosis event (first and recurrent) from randomization until the efficacy cutoff	Andersen-Gill model ^a	ITT	Censor

AVG=arteriovenous graft; ITT=Intent-to-Treat (all randomized participants).

9.6.2 Analysis Methods for Safety Analyses

Safety and tolerability will be assessed by clinical review of all relevant parameters including AEs, laboratory tests, vital signs, and ECGs. The primary approach to analysis of safety will include all data through treatment including the 3-month follow-up assessment. The analysis will compare safety events in each MK-2060 group to the placebo group.

^a Treatment group and the stratification factors used for randomization will be included in the model as fixed effects.

Adverse Events

AEs will be coded using the standard MedDRA and grouped according to SOC.

The analysis of safety results will follow a tiered approach (Table 4). The tiers differ with respect to the analyses that will be performed.

For the safety analyses, any participant who undergoes a kidney transplant during the study will be censored at 3 months after the date of the kidney transplant.

Tier 1 Events

Safety parameters or AEs of special interest that are identified a priori constitute "Tier 1" safety endpoints that will be subject to inferential testing for statistical significance with p-values and 95% CIs. For this protocol, the time to the composite endpoint of an ISTH major bleeding event or a clinically relevant non-major bleeding event (adjudicated) is a Tier 1 event and will be analyzed following the analysis approach for the primary efficacy analysis.

Tier 2 Events

Tier 2 parameters will be assessed via point estimates with 95% CIs provided for between-treatment differences in the proportion of participants with events.

Membership in Tier 2 requires that at least 4 participants in any treatment group exhibit the event; all other AEs and PDLCs will belong to Tier 3. The threshold of at least 4 events was chosen because the 95% CI for the between-group difference in percent incidence will always include zero when the treatment groups each have fewer than 4 events and thus would add little to the interpretation of potentially meaningful differences. Because many 95% CIs may be provided without adjustment for multiplicity, the CIs should be regarded as a helpful descriptive measure to be used in review, not a formal method for assessing the statistical significance of the between-group differences in AEs and PDLCs.

[figure not shown]
In addition, summary measures of AEs consisting of the percentage of participants with any AE, with a drug-related AE, with an SAE, with an AE which is both drug-related and serious, who discontinued due to an AE, and who died will be considered Tier 2 endpoints.

For AEs prespecified for adjudication (cardiovascular, AVG thrombotic, bleeding events, and death), results of adjudication are also considered Tier 2 endpoints.

The 95% CIs will be provided for between-treatment differences in the percentage of participants with each Tier 2 event; these analyses will be performed using the M&N method.

Tier 3 Events

Safety endpoints that are not Tier 2 events will be considered Tier 3 events. Only point estimates by treatment group will be provided for Tier 3 safety parameters.

Continuous Safety Measures

For continuous measures such as changes from baseline in laboratory and vital signs parameters, summary statistics for baseline, on treatment, and change from baseline values will be provided by treatment group.

Table 4 Analysis Strategy for Safety Parameters

[figure not shown]
Safety Tier	Safety Endpoint	P-Value for Treatment Comparison	95% CI for Treatment Comparison	Descriptive Statistics
Tier 1	Time to first ISTH major bleeding event or clinically relevant non-major bleeding event (adjudicated)	X	X	X
Tier 2	Any AE		X	X
	Any serious AE		X	X
	Any drug-related AE		X	X
	Any serious and drug-related AE		X	X
	Discontinuation due to AE		X	X
	Death		X	X
	Adjudicated major thrombotic CV events		X	X
	Adjudicated AVG thrombotic events		X	X
	Adjudicated ISTH major bleeding events		X	X
	Specific AEs, SOCs, PDLCs (incidence ≥4 of participants in 1 of the treatment groups)		X	X
Tier 3	Specific AEs, SOCs, PDLCs (incidence <4 of participants in all the treatment groups)			X
	Change from baseline results (laboratory tests, ECGs, vital signs)			X

AE=adverse event; AVG=arteriovenous graft; CI=confidence interval; CV=cardiovascular; ECGs=electrocardiogram(s); ISTH=International Society on Thrombosis and Haemostasis; PDLC=predefined limit of change; SOC=system organ class; X=results will be provided.

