8. The participant interrupted study intervention for >4 consecutive doses and is not a candidate for reloading after consultation with the Sponsor (refer to the Operations Manual for reloading).

Any time a participant's vital status is in question, the investigator should explore all possible options to contact the participant per local regulations (unless the participant has explicitly withdrawn his/her consent to any type of follow-up). The site must document all attempts to try to contact the participant in the medical records/source documents. The vital status will be collected for all randomized participants who have not withdrawn consent, irrespective of completion of study procedures.

If the participant does not attend scheduled study visits, follow-up of clinical events specified as endpoints may continue by phone, unless the participant explicitly withdraws his/her consent to any type of follow-up. In such cases, the phone contact will not be considered a protocol deviation.

In all cases, the reason for temporary interruption or permanent study intervention discontinuation must be recorded in the eCRF and in the participant's medical records.

Participants may be allowed to begin treatment again if deemed medically appropriate.

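### Death, and ISTH major bleeding on its own, are compared only as percentages, and the safety data window for participants who stop early is ambiguous

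*Combined protocol and SAP*

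**What the plan says.** Section 9.6.2 places death in Tier 2 among the summary measures: participants "who discontinued due to an AE, and who died will be considered Tier 2 endpoints". Table 4 gives "Adjudicated ISTH major bleeding events" its own Tier 2 row. The comparison is the same throughout Tier 2: "The 95% CIs will be provided for between-treatment differences in the percentage of participants with each Tier 2 event", and "these analyses will be performed using the M&N method". There is no p-value, and the section calls these intervals descriptive.

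Major bleeding also counts towards the Tier 1 endpoint, time to first ISTH major or clinically relevant non-major bleed, which "will be analyzed following the analysis approach for the primary efficacy analysis", that is, by stratified log-rank test and Cox model.

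Two rules govern which data enter:

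- Transplant: "any participant who undergoes a kidney transplant during the study will be censored at 3 months after the date of the kidney transplant". Section 4.1 applies this to all safety analyses.
- Window: "The primary approach to analysis of safety will include all data through treatment including the 3-month follow-up assessment". Section 9.6 ends the primary safety data at the Safety Follow-up Visit and adds a supportive summary through the efficacy cutoff.

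Participants who stop treatment early have their own Safety Follow-up Visit, about 3 months after the last dose (8.11.6) or 90 days after the discontinuation visit (8.11.7). The Schedule of Activities then keeps them on 3-monthly visits to the Final Efficacy Visit, with clinical events, AEs and vital status collected. Section 7.1 adds: "The vital status will be collected for all randomized participants who have not withdrawn consent, irrespective of completion of study procedures".

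**The concern.** The trial is event-driven, so follow-up varies by design, and the plan orders censoring in its safety analyses. A difference in proportions has no censoring. A participant whose data end at month 4 and one followed event-free to month 18 contribute the same zero. If follow-up is shorter in one arm, that arm shows fewer deaths at the same hazard.

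The window raises a different question. Read literally, an early stopper's primary safety data end at their own 3-month visit, and a death after it would count as a non-event. The supportive summary through the efficacy cutoff would include that death, but it omits deaths between the cutoff and the last safety visit. On this reading no planned summary holds every death.

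Mandatory reasons to stop in Section 7.1 include a major non-traumatic bleed, ongoing prohibited medication and permanent loss of the graft as access. An anticoagulant may change how often these occur, so the length of counted follow-up could depend on treatment and prognosis. Mortality and major bleeding are what a reader will weigh against fewer graft thromboses. The eDMC may recommend continuing after a positive interim result on bleeding grounds, and the trial is meant to inform dose selection.

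**Working it through.** **Inputs from the documents.** 163 participants per arm; median treatment about 10 months; about 20 months from first enrolment to last visit; safety follow-up 3 months.

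**Assumptions.** The documents give no death, stopping or transplant rates, so ranges are used. Time from entry to cutoff is uniform on 3 to 17 months: the median is (3 + 17)/2 = 10 months, and the longest stay is 17 + 3 = 20 months, matching the plan. With 3 months of safety follow-up, completers are observed for 6 to 20 months.

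**1. The plan's own figures.** The M&N score interval (variance factor N/(N−1), 163 per arm) gives:

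| Counts | 95% CI for the difference |
|---|---|
| 4 v 0 | 0.12% to 6.15% |
| 9 v 2 | 0.44% to 9.10% |
| 24 v 12 | 0.57% to 14.46% |
| 3 v 0 | −0.49% to 5.28% |

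Table 8 and the threshold of 4 events for Tier 2 reproduce. No stated figure is wrong.

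**2. Follow-up that differs between arms.** With yearly hazard h and follow-up uniform on a to b months, the expected crude percentage is

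P = 1 − 12/[h(b − a)] × [exp(−ha/12) − exp(−hb/12)].

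For h = 0.15: 14.89% on 6 to 20 months, and 13.52% on 5.4 to 18 months (10% shorter), a difference of −1.37 points although the hazard ratio is 1. Over the range:

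| Deaths per 100 patient-years | 10% shorter | 20% shorter | 30% shorter |
|---|---|---|---|
| 5 | −0.51 | −1.03 | −1.55 |
| 10 | −0.97 | −1.95 | −2.94 |
| 15 | −1.37 | −2.77 | −4.19 |
| 20 | −1.73 | −3.51 | −5.32 |

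With equal follow-up the difference is 0.

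**3. Transplant rule.** At 15 deaths per 100 patient-years and 2 to 10 transplants per 100 patient-years, ignoring deaths more than 3 months after transplant lowers the crude percentage from 14.79 to 14.69 (lowest rate) and from 14.87 to 14.36 (highest), about 0.1 to 0.5 points.

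**4. Window.** Simulation with exponential death and stopping. Early stoppers are followed either to the cutoff (all visits) or only to 3 months after stopping (closed window); completers to cutoff plus 3 months. At 15 deaths per 100 patient-years:

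| Stopping by 12 months | Mortality ratio after stopping | All deaths | Closed window | Share left out |
|---|---|---|---|---|
| 15% | 1 | 14.4% | 13.9% | 3.4% |
| 15% | 2 | 15.4% | 14.5% | 5.6% |
| 30% | 1 | 14.1% | 13.2% | 6.8% |
| 30% | 2 | 15.8% | 14.1% | 11.3% |
| 45% | 1 | 13.8% | 12.3% | 11.0% |
| 45% | 2 | 16.4% | 13.5% | 17.3% |

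Across 10 to 20 deaths per 100 patient-years the share is about 3% to 18%. In this table that is 163 × 0.005 = 0.8 to 163 × 0.029 = 4.7 deaths per arm. A second set of assumptions (11-month enrolment, cutoff at 17.3 months, 20% to 40% stopping per year, ratio 1 to 3) gives 4.7% to 18.2%.

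**5. Between arms.** Take 30% stopping in one arm and 15% in the other, 10 to 20 deaths per 100 patient-years:

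- Ratio 1: crude difference −0.3 to −0.5 points on all visits and −0.7 to −1.2 on the closed window, although hazards are equal. Mean follow-up is 12.4 v 12.7 months and 11.5 v 12.3 months, so this scenario stays below the 10% column in step 2.
- Ratio 2: +0.4 to +0.7 points on all visits becomes −0.3 to −0.5 on the closed window. The sign changes, but the shift is only about 0.7 to 1.2 points.

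The Monte Carlo standard error of a difference is about 0.1 point: √(2 × 0.15 × 0.85/400,000) = 0.0008.

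For scale, the 95% CI half-width at 163 per arm is 1.96 × √(2 × 0.10 × 0.90/163) = 6.5 points at 10% mortality and 1.96 × √(2 × 0.15 × 0.85/163) = 7.8 points at 15%.

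**The case against.** Several stronger readings are tempting, and the documents do not support them.

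- A reader might infer that major bleeding is never analysed over time. It is part of the Tier 1 composite, where the transplant censoring works as written. What stands is narrower: Section 4.2.1.3 lets any bleed that prompts a face-to-face evaluation into the composite, so non-major events may dominate it, and major bleeding alone has only a percentage.
- A reader might infer that unequal follow-up as such biases the comparison. Staggered entry affects concurrently randomized 1:1:1 arms alike; bias needs follow-up that differs by arm.
- A reader might blame M&N for lost deaths. A Cox model on the same closed window would not count them either.
- A reader might conclude that the plan excludes late deaths. No section says so. Section 9.6 can be read at trial level, with a second database lock once all safety follow-up is in, and Sections 7.1, 8.4.1 and 8.11.6 keep events coming in after an early stop. What stands is that 8.11.6 and 8.11.7 give early stoppers a Safety Follow-up Visit of their own, so the sentence ending primary data at that visit has two meanings.
- A participant stopped for a major bleed already counts in the major-bleeding percentage; closing the window cannot remove that event. The concern about early stopping therefore applies mainly to death.

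It is also fair that Tier 2 intervals are labelled descriptive, that the transplant effect is small, and that a shift of about 1 point is well inside the interval. These limit the importance of the point. They do not supply a survival analysis of death.

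**Conclusion.** The point holds in a limited form. For death, and for adjudicated ISTH major bleeding taken alone, the plan names only a difference in percentages. That method cannot censor in the ordinary sense and ignores follow-up that differs between arms. Separately, the primary safety window needs one clear meaning for early stoppers.

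The size rests on assumed rates. About 3% to 18% of deaths could fall outside the window if it closes 3 months after stopping. With 30% against 15% stopping, the crude death difference moves by about 1 point or less in most cases and 1.2 at most. Larger errors, up to 5.3 points, need 30% less follow-up in one arm and 20 deaths per 100 patient-years, which the stopping scenarios do not produce. Transplant censoring matters least, at 0.1 to 0.5 points.

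This is a cheap improvement to method and wording. It does not show that the planned safety comparison is invalid.

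**What to change.** 1. Keep the Tier 2 rows as descriptive summaries.
2. Add time from randomization to death from any cause in all randomized participants, through the last known vital-status date and regardless of treatment stopping: Kaplan-Meier by arm and Cox HR with 95% CI, with sparse strata combined as Section 9.6 already allows.
3. Add time to first adjudicated ISTH major bleed with the Tier 1 model and the stated transplant censoring.
4. State in Sections 9.6 and 9.6.2 that events after early discontinuation count through the participant's last study contact.
5. State whether transplant censoring applies to death, and how it enters the Tier 2 percentages.

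The cost is SAP wording and two outputs from data already collected. The mortality analysis will include off-drug time and use all randomized participants, so it will not match the APaT row exactly and both should be labelled. If events are few, the intervals will be wide.
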